7.2.1. Withdrawal of Consent

Participants who request to discontinue receipt of study intervention will remain in the study and must continue to be followed for protocol-specified follow-up procedures. The only exception to this is when a participant specifically withdraws consent for any further contact with them or persons previously authorized by the participant to provide this information. Participants should notify the investigator in writing of the decision to withdraw consent from future follow-up, whenever possible. The withdrawal of consent should be explained in detail in the medical records by the investigator, as to whether the withdrawal is only from further receipt of study intervention or also from study procedures and/or posttreatment study follow-up, and entered on the appropriate CRF page. In the event that vital status (whether the participant is alive or dead) is being measured, publicly available information should be used to determine vital status only as appropriately directed in accordance with local law.

7.3. Lost to Follow-Up

A participant will be considered lost to follow-up if the participant repeatedly fails to return for scheduled visits and is unable to be contacted by the study site.

The following actions must be taken if a participant fails to attend a required study visit:

- The site must attempt to contact the participant and reschedule the missed visit as soon as possible. Counsel the participant on the importance of maintaining the assigned visit schedule, and ascertain whether the participant wishes to and/or should continue in the study;
- Before a participant is deemed lost to follow-up, the investigator or designee must make every effort to regain contact with the participant (where possible, 3 telephone calls and, if necessary, a certified letter to the participant's last known mailing address or local equivalent methods). These contact attempts should be documented in the participant's medical record;
- Should the participant continue to be unreachable, the participant will be considered to have withdrawn from the study.

8. STUDY ASSESSMENTS AND PROCEDURES

8.1. Administrative and Baseline Procedures

The investigator (or an appropriate delegate at the investigator site) must obtain a signed and dated ICD before performing any study-specific procedures.

Study procedures and their timing are summarized in the [SoA](#). Protocol waivers or exemptions are not allowed.

Adherence to the study design requirements, including those specified in the [SoA](#), is essential and required for study conduct.

All screening evaluations must be completed and reviewed to confirm that potential participants meet all eligibility criteria. The investigator will maintain a screening log to record details of all participants screened and to confirm eligibility or record reasons for screening failure, as applicable.

Every effort should be made to ensure that protocol-required tests and procedures are completed as described. However, it is anticipated that from time to time there may be circumstances outside the control of the investigator that make it unfeasible to perform the test. In these cases, the investigator must take all steps necessary to ensure the safety and wellbeing of the participant. When a protocol-required test cannot be performed, the investigator will document the reason for the missed test and any corrective and preventive actions that they have taken to ensure that required processes are adhered to as soon as possible. The study team must be informed of these incidents in a timely manner.

For samples being collected and shipped, detailed collection, processing, storage, and shipment instructions and contact information will be provided to the investigator site prior to initiation of the study.

The minimum total blood sampling volume for individual participants in this study is approximately 70 mL and 90 mL for the approximately ~~CCI~~ participants providing additional PK samples. Additional blood samples may be taken for safety or eligibility assessments at times specified in the [SoA](#), provided the total volume taken during the study does not exceed 550 mL during any period of 56 consecutive days.

Participants must have a positive RSV test before enrollment into the clinical study. RSV, SARS-CoV-2, and influenza diagnostic tests or other procedures conducted as part of the participant's standard of care and obtained before signing of the ICD may be utilized for eligibility review purposes provided the procedures met the protocol-specified criteria and were performed within the time frame defined in the [SoA](#). If a participant does not have access to obtain an RSV test, please see [Section 5.4](#) for the pre-screening procedure informed consent option.

Participants in the United States will be invited to provide informed consent to participate in optional, additional research using real world data to describe long-term health outcomes and healthcare utilization (see [Section 10.10.1](#))

8.1.1. Baseline Procedures

Medical history in addition to RSV disease history and demographics will be collected at screening. Smoking status will be collected.

Complete medication history of all prescription or nonprescription drugs (including vaccinations), and dietary and herbal supplements taken within 30 days prior to the planned first dose will be collected. RSV-related vaccinations and monoclonal antibody for the treatment or prevention of RSV at any time prior to randomization will also be collected. Medications causing ongoing immunosuppressant effect, such as biologics or cancer

treatments, administered at any time prior to randomization will be collected. Risk factors for the participant developing severe RSV illness will be recorded.

Viral Screening Assessment for Study Eligibility

If the participant fails to provide a negative test for SARS-CoV-2 and influenza within 7 days of randomization, a specimen will be collected at screening for viral testing of SARS-CoV-2 and/or influenza. Viral testing of SARS-CoV-2 and/or influenza will be performed according to the manufacturer information for use. Some testing equipment will simultaneously test this nasal swab for RSV, and a negative RSV result from this test will exclude the participant from the study.

8.1.2. Telehealth Visits

Telehealth visits may be used to assess participant safety and collect data points. Telehealth includes the exchange of healthcare information and services via telecommunication technologies (eg, audio, video, videoconferencing software) remotely, allowing the participant and the investigator to communicate on aspects of clinical care, including medical advice, reminders, education, and safety monitoring. Assessments that may be performed during a telehealth visit are described in the [SoA](#).

Study participants must be reminded to promptly notify site staff about any change in their health status.

8.2. Efficacy Assessments

8.2.1. RSV-related hospitalizations and Medical Details

Details of participants' RSV-related medical visits (ie, hospitalization of any duration, urgent care, emergency room) will be collected during study visits, including level of care (ICU status), dates of utilization (including admission and discharge), and discharge status, as applicable.

For the primary endpoint, hospitalization of at least 24 hours of acute care is defined as ≥ 24 hours of acute care in a hospital or similar acute care facility. This includes specialized acute medical care unit within an assisted living facility or nursing home. Participants who are waiting in an emergency department or other hospital unit for an inpatient bed to become available are considered hospitalized provided that a decision to admit to inpatient care has occurred. For the secondary endpoint of RSV-related visits (urgent care/ED/hospital) or death from any cause, no minimum duration of hospitalization is required.

Investigators will determine if a medical visit is related to RSV. For reference, RSV related medical visits are those attendances that would not otherwise occur in the absence of the RSV infection. These may include visits for: deterioration or decompensation of the lung function that require supplemental oxygen; development of secondary respiratory tract infections that require antibiotic treatment; management of severe symptoms associated with RSV such as fever; worsening or decompensation of cardiac or renal function in patients with underlying cardiac or renal disease.

8.2.2. Survival status

Information about the death of a participant may be collected from death registries, hospital databases, other healthcare professionals, from participant's legal representatives, or other persons authorized by the participant and according to local regulations. The death of a participant cannot be assumed by their non-responsiveness, as the participant may be lost to follow-up.

8.2.3. Clinical response

Clinical response is evaluated by the investigator at Day 5, 10, 15, and 28 visits using the criteria for ARI in Table 2 that were required for study entry.

Table 2. Criteria for ARI

ARI is defined as the presence of 1 or more of the following signs and symptoms:

- New or increased nasal congestion.
- New or increased nasal discharge.
- New or increased sore throat.
- New or increased cough.
- New or increased sputum production.
- New or increased shortness of breath.
- New or increased wheezing.

The outcome of this assessment will be recorded in the CRF as one of the following categories:

- Resolution – All ARI signs or symptoms are absent or have returned to pre-infection status.
- Improvement – No new ARI signs or symptoms, and no worsening of existing signs or symptoms compared to the Day 1 visit. At least one sign or symptom (but not all) present at Day 1 is absent, improved or has returned to pre-infection status.
- No change – No change in the ARI signs or symptoms compared to the Day 1 visit.
- Worsening – New or worsening in severity of at least one ARI signs or symptom compared to the Day 1 visit.

8.2.4. RSV-related lower respiratory tract infection

Signs and symptoms of RSV will be collected by the Investigator per the [SoA](#) (Section 1.3) during scheduled visits. Criteria for diagnosis of LRTI are provided in Table 3. Criteria for diagnosis of severe LRTI (sLRTI) are provided in [Table 4](#) [14]. Intensity grading displayed in [Table 5](#) is a component of the severe LRTI criteria. An episode of LRTI that does not meet criteria for sLRTI is considered non-severe LRTI (nsLRTI). Investigators will determine if sLRTI or nsLRTI is related to RSV (referred to as sLRTI-RSV and nsLRTI-RSV).

- Development of LRTI is defined as transitioning from not having LRTI at randomization to having nsLRTI-RSV or sLRTI-RSV.
- Progression of LRTI is defined as development of LRTI or transitioning from nsLRTI-RSV at randomization to sLRTI-RSV.
- Resolution of LRTI is defined as transition from nsLRTI-RSV or sLRTI-RSV at randomization to not having nsLRTI-RSV and not having sLRTI-RSV.
- Improvement in LRTI status is defined as LRTI resolution or transition from sLRTI-RSV at randomization to nsLRTI-RSV.

Table 3. Criteria for LRTI

LRTI is defined as:	

• ≥ 2 lower respiratory signs or symptoms for at least 24 hours including at least 1 lower respiratory sign;	
Or	

• 3 lower respiratory symptoms for at least 24 hours.	
Lower respiratory symptoms	Lower respiratory signs

• New or increased sputum.• New or increased cough.• New or increased dyspnea (shortness of breath).	
• New or increased wheezing.• New or increased crackles/ronchi based on chest auscultation.• Respiratory rate ≥ 20 respirations/minute.• Low or decreased oxygen saturation ($O_2 < 95\%$ or $\leq 90\%$ if pre-season baseline is $< 95\%$).• Need for new or increased oxygen supplementation.

Table 3. Criteria for LRTI

LRTI is defined as:

• ≥ 2 lower respiratory signs or symptoms for at least 24 hours including at least 1 lower respiratory sign;
Or

• 3 lower respiratory symptoms for at least 24 hours.

Criteria for LRTI are based on Papi, et al. 2023 [14].

Table 4. Criteria for severe LRTI

Severe LRTI is defined as the presence of LRTI with at least one of the following criteria:

• ≥ 2 lower respiratory signs.

• An LRTI episode assessed as ‘severe intensity’ by investigator per intensity grading in Table 5.

• Need for hospitalization.

• Need for positive airway pressure therapy (eg, CPAP).

• Need for other types of mechanical ventilation.
Lower respiratory signs:

• New or increased wheezing.

• New or increased crackles/ronchi based on chest auscultation.

• Respiratory rate ≥ 20 respirations/minute.

• Low or decreased oxygen saturation ($O_2 < 95\%$ or $\leq 90\%$ if pre-season baseline is $<95\%$).

• Need for new or increased oxygen supplementation.

Criteria for severe LRTI are based on Papi, et al. 2023[14].

Table 5. Intensity grading for LRTI

Mild intensity	An LRTI episode which is easily tolerated by the participant causing minimal discomfort and not interfering with everyday activities* or self-care**.
Moderate intensity	An LRTI episode which is sufficiently discomforting to interfere with everyday activities* but does not interfere with self-care**.
Severe intensity	An LRTI episode which prevents everyday activities* and interferes with self-care.**

Intensity grading for LRTI are based on Papi, et al. 2023 [14].

* Everyday activities include housework, work, family activities, or leisure activities. Interference in everyday activities must be due to signs and symptoms of the acute respiratory infection and not solely due to viral infection quarantining/isolation considerations.

**Self-care includes feeding, bathing, grooming, dressing, and toileting.

Change of everyday activities and self-care should be compared to each patient's baseline status. For example, a previously mobile participant becoming bed bound would be an example of severe LRTI.

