Randomization			X									
 It is preferable for screening and randomization to occur on the same day. If screening occurs over 2 consecutive days, randomization must occur on the second day. Randomization and treatment start on the same day. At randomization, the participant enrolment number is assigned.
Medical History and Physical Examination												
Medical History		X										
Physical examination		X	X								X	
 Physical examination at days 3, 5, 10, 15, 28, 35, and the unplanned visit to be performed at discretion of the investigator. Physical examinations to be completed before administration of study intervention. A general physical examination is to be performed at screening/baseline on all participants, thereafter symptoms' driven. If screening and randomization happen on the same day, examination performed only once. See Section 8.3.1 for additional information.

Table 1. Study Schedule of Activities

Visit Identifier Abbreviations may be found in Appendix 11 . X = required	Pre- screen (Optional)	Screen	Treatment Period			F/U					Early Discont.	Notes
			Day 1	Day 3	Day 5	Day 10	Day 15	Day 28	Day 35	Unplanned Visit for Post- Treatment ARI (in-person)		
Visit Window	Day -4 to 1	Day -1 to 1	(0)	(±1)	(+1)	(± 1)	(± 2)	(± 2)	(± 2)	Day 6 to 28		
 See Section 8.4.3 for follow-up AE and SAE assessments.
Record signs and symptoms to confirm LRTI status		X	X	X	X	X	X	X		X	X	
 If screening and randomization happen on the same day, LRTI status is assessed only once on Day 1.
Assess clinical response					X	X	X	X				
 See Section 8.2.3.
Weight, height		X										
 See Section 8.3.1 for additional information.
Vital signs		X	X	X	X	X	X	X		X	X	
 If screening and randomization happen on the same day, vital signs are collected only once. Vital signs at day 35 visit to be performed at discretion of the investigator. See Section 8.3.2 for additional information.
12-Lead ECG		X										
 ECG to be performed after screening only as needed per investigator discretion. See Section 8.3.3 for additional information.
Contraception check		X	X	X	X	X	X	X	X	X	X	

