5.1. Inclusion Criteria

Participants are eligible to be included in this study only if all of the following criteria apply:

Age and Sex:

1. Participants aged 18 years or older (or the minimum age of consent, if above 18, in accordance with local regulations) at screening.
 - Women of childbearing potential must agree to use highly effective contraception. Refer to [Appendix 4](#) (Section 10.4.3 and 10.4.4) for reproductive criteria for female participants.

Disease Characteristics:

2. Diagnosis of RSV infection, as determined by a positive RT-PCR, rapid antigen test, or other locally available diagnostic test in any respiratory specimen (eg, nasal,

PFIZER CONFIDENTIAL

CT02-GSOP Clinical Protocol Template Phase 1 2 3 4 (14 April 2023)

Page 46

nasopharyngeal swab, sputum) collected within 5 days of randomization. Randomization must occur no later than the 5th day since the diagnosis of RSV infection where the day of RSV diagnosis is the 1st day.

3. New onset or worsening (if present chronically) of at least one of the following signs and/or symptoms consistent with a viral acute respiratory infection (ARI), within 5 days prior to randomization: nasal congestion, nasal discharge, sore throat, cough, sputum production, shortness of breath, or wheezing. Randomization must occur no later than the 5th day, where the day of onset/worsening is the 1st day.

Other Inclusion Criteria:

4. Has at least 1 of the following characteristics or underlying medical conditions:
 - 65 years of age or older.
 - Chronic lung disease that is symptomatic or requiring treatment, including but not limited to: COPD, asthma, CF, PF, PAH, alpha-1 anti-trypsin deficiency, or pulmonary sarcoidosis.
 - Heart failure (functional class II-IV according to NYHA classification).
 - Immunosuppressive disease or condition (eg, hematological malignancy, CAR-T, bone marrow or organ transplant recipient, primary immune deficiency, or HIV infection with CD4+ cell count <200 / μ L within the last 6 months) OR use of at least 1 of the following immune-weakening medications:
 - Recent treatment with corticosteroids equivalent to prednisone \geq 20 mg daily for at least 14 consecutive days, all of which must have been within the last 30 days prior to study entry OR are currently receiving \geq 20 mg daily that must have been administered for at least 14 consecutive days at the time of study entry.

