8.3.2. Vital Signs

Temperature, pulse rate, respiratory rate, oxygen saturation level, and blood pressure will be assessed as specified in [Table 1](#).

Any untoward vital sign findings that are identified during the active collection period and meet the definition of an AE or SAE ([Appendix 3](#) in [Section 10.3](#)) must be reported according to the processes in [Sections 8.4.1](#) to [8.4.3](#).

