## 2.1. Modifications to the Analysis Plan Described in the Protocol

This study was discontinued due to business reasons, with very few participants enrolled. There were no safety concerns in the decision to stop the study and no changes to the sponsor's assessment of the risk-benefit profile for participants who received sisunatovir in the study.

The amended SAP will therefore focus on descriptive summaries of the primary and key secondary efficacy endpoints and safety summaries.

In sections 3, 9.1.1.2, and 9.3.3 of the protocol, the LRTI estimands and endpoints are generally mentioned in terms of RSV-related LRTI, eg, nsLRTI-RSV. The SAP modifies these endpoints to analyze all-cause LRTI, regardless of the investigator assessment of RSV-relatedness. The direct and indirect impact of RSV on underlying LRTI disease may be difficult to assess. The criteria for severe LRTI are pre-specified and adding the investigator subjective assessment may be confounding.

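### Does the undefined pre-season baseline for oxygen saturation leave the LRTI endpoints without a usable rule?

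*Protocol*

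**What the plan says.** Protocol Section 8.2.4 lists low or decreased oxygen saturation as one of five lower respiratory signs, in Table 3 (LRTI) and again in Table 4 (severe LRTI). The limit is a reading below 95%, or 90% or less "if pre-season baseline is" below 95%. The phrase occurs only in those two tables. No footnote, abbreviation entry or SAP section explains it, and no redaction touches it.

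Several other places bear on the point:

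- **Entry (Protocol 5.1).** Criterion 3 says "Randomization must occur no later than the 5th day, where the day of onset/worsening is the 1st day". Criterion 4 admits, among others, "Chronic lung disease that is symptomatic or requiring treatment, including but not limited to: COPD, asthma, CF, PF, PAH" and NYHA class II-IV heart failure.
- **Collection (Protocol 1.3, 8.3.2, 8.1.1).** The Schedule of Activities has a row headed "Record signs and symptoms to confirm LRTI status". Vital signs start at screening (Day -1 to 1), with the note "If screening and randomization happen on the same day, vital signs are collected only once". Section 8.3.2 says "Temperature, pulse rate, respiratory rate, oxygen saturation level, and blood pressure will be assessed as specified in" Table 1. Section 8.1.1 says "Medical history in addition to RSV disease history and demographics will be collected at screening" and does not name a usual saturation.
- **Analysis (SAP 3.5, 3.2.1.1, 2.1).** The baseline window for vital signs and LRTI is Day -2 to Day 1. The analysed classification is the investigator's non-severe or severe entry on the CRF. SAP 2.1 moves to all-cause LRTI and gives as one reason: "The criteria for severe LRTI are pre-specified and adding the investigator subjective assessment may be confounding".

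**The concern.** The limit for one sign depends on a value that the trial's own schedule cannot supply. Participants enter with symptoms already present, so no scheduled reading predates the illness. Tables 3 to 5 are stated to be based on a report that is, by its title, of an RSV vaccine trial in older adults, and the wording may have come with the criteria. Criterion 4 admits the kind of participant whose usual saturation may be below 95%.

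LRTI status at randomization decides who enters each LRTI analysis set, and later status is the outcome for progression, development and resolution. Progression through Day 10 is also the one key secondary endpoint with its own power statement in Protocol Section 9.5. If sites chose the reference differently, a stable reading of 91-94% could count as a sign at every visit, which treatment could not clear. In the other direction, a screening reading of 93% taken as the baseline could hide a real fall. The SAP's reliance on pre-specified criteria would then look misplaced.

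**Working it through.** The plan gives no figure for this point, so there is nothing to reproduce. The check applies the printed rule case by case and then asks how far it leaves the classification open.

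**1. The rule by what is known of the usual value** (whole-number readings):

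| Usual value before the illness | Limit on a plain reading | Reading of 91-94% |
|---|---|---|
| Known, 95% or more | below 95% | sign |
| Known, below 95% | 90% or less | not a sign |
| Unknown | below 95% (general limit; exception not triggered) | sign |

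Readings of 90% or less, or of 95% or more, give the same answer in every row.

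**2. The two harmful cases against the rule.** A participant with a stable, known usual value of 91-94% falls in the second row, so the reading is not a sign. It becomes a permanent sign only if the exception is ignored or the value is unknown. In the opposite case, a reading taken after symptom onset is treated as a pre-season value, which the words exclude. Season also has a natural meaning here: Protocol Section 5.5 speaks of rescreening in the following RSV season.

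**3. Where the sign changes the class.** From Tables 3 and 4, assuming every finding meets the 24-hour condition and using only the sign-count route to severe LRTI:

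- LRTI = (signs + symptoms ≥ 2 with signs ≥ 1) or 3 symptoms.
- Severe = LRTI with signs ≥ 2.

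The other 4 signs and 3 symptoms give 2^7 = 128 patterns.

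| Saturation sign | No LRTI | Non-severe | Severe |
|---|---|---|---|
| Absent | 11 | 29 | 88 |
| Present | 1 | 7 | 120 |

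The class changes in 28 + 6 + 4 = 38 patterns: 28 from non-severe to severe, 6 from none to non-severe, and 4 from none to severe. It never changes when two or more other signs are present. At Day 15, for example, a reading of 93% with one residual symptom and no other sign is resolved under the lower limit (0 signs, 1 symptom) and not resolved under the general one (1 sign + 1 symptom = 2).

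These counts do not measure the problem. The enumeration switches one sign on or off, so by symmetry any of the five signs would give the same 38 of 128. It also weights all patterns equally, although low saturation and a need for new oxygen plainly go together.

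**4. What has to coincide.** With the rule read as in step 1, the open share of participants is

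P(usual value below 95%) × P(unknown to the site, given that) × P(reading 91-94%, given those) × P(other findings at a class boundary, given those).

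None of these four factors is given in the documents.

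**5. Where a site would find the value.** Medical history is taken at screening (Protocol 8.1.1). Section 10.1.8 notes that investigators may need to request previous medical records. Section 8.3.2.3 has participants on chronic oxygen measured while on it, which may reduce the number with a low stable reading. CRF completion guidance (10.1.7) and endpoint derivations (SAP Appendix 2.2) sit in documents that were not available here.

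**6. The SAP sentence.** SAP 2.1 explains why one further layer, the judgement of RSV-relatedness, is dropped. It does not say that the criteria are free of judgement. Table 4 itself includes investigator-graded severe intensity and need for hospitalization, so there is no contradiction.

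**The case for a change.** The best case for a change is that the gap is real and cheap to close: one definition and one screening field with its source. The protocol uses three reference terms without linking them: the pre-season value for saturation, pre-infection status for clinical response (Section 8.2.3), and each patient's baseline status for daily activities (Table 5 notes). The people the exception is meant for belong to the target population, and the LRTI endpoints are still summarised under SAP version 2.

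The textual part of this stands: the term is undefined in both documents, and no scheduled reading supplies it. The step from there to harm does not. The printed rule already covers the known cases, and a plain reading covers the unknown one. A definition would mostly write down what a careful investigator would do, namely use the participant's usual saturation before this illness. It would not remove the unknown cases. Nor do the documents support a statement that the reference was never defined for sites, since the CRF, its completion guidance and the Analysis and Reporting plan have not been seen.

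**Conclusion.** No change follows. This is missing detail on the source of one reference value, of a kind investigators can fill sensibly.

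The classification is unaffected for readings of 90% or less or 95% or more, where the usual value is known and the rule is applied as printed, and wherever two or more other signs are present. For the remainder, the frequency cannot be computed from the documents. Because the study is randomized and double-blind, and the usual value predates treatment, any misclassification should be similar in the two arms: noise or dilution rather than bias between them. The primary endpoint does not use the sign. The study stopped with very few participants, and SAP Section 5.1 rules out inferential testing, so no test result depends on it.

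The conclusion assumes that below 95% is read as the general limit, that sites do not treat a reading taken during illness as pre-season, and that the 24-hour condition is met. If the same tables were used in another protocol, aligning the term with the pre-infection wording of Section 8.2.3 would be a reasonable editorial clarification.
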